4.5 Aortix Post-Deployment Monitoring and Management

The Aortix Pump has been tested to operate safely for 7 days of use. Aortix therapy should continue until objective signs of hemodynamic congestion have resolved, alternative / escalated therapy is required, or if device related safety concerns arise. The duration of Aortix pump use should be dictated by the physician's target for diuresis (net fluid and weight loss). In addition, the pre-specified target for pump effectiveness is a **minimum 20%** decrease in the patient's CVP and PCWP from pre-implant. **Diuretics and inotropes should not be adjusted for twelve (12) hours after the Aortix pump is turned on. After that point, while the Aortix pump is running, cessation of medications or down titration of diuretics, inotropes or other heart failure medications are allowed.** Adjustments of other medical therapy can otherwise be made at any point during the study period at the discretion of the treating physician. All medications and medications adjustments will be captured on eCRFs.

Refer to the Aortix System Instructions for Use (PPL004) for details of the Aortix Pump management.

If clinically significant device migration is suspected, use x-ray or another imaging modality to verify pump position.

It is recommended that the patient's vital signs be monitored frequently post procedurally (e.g., vitals checked every 15 minutes for the first hour, then every 30 minutes for the second hour). The patient's pedal pulses should be monitored post procedurally frequently for distal limb perfusion, ideally but not limited to, every fifteen (15) minutes times four (4), every thirty (30) minutes times two (2) and every hour (1) for two (2) hours and then as frequently as signs and symptoms warrant. In addition, the access site should be monitored for bleeding, hematoma, swelling or signs of infection.

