4.5.3 Congestion Target Met/Therapy Deemed Ineffective Data Collection

Once the congestion target has been met or therapy has been deemed ineffective, before weaning begins, the following assessments should be made within 12 hours of beginning weaning:

- Cardiovascular exam (edema, pulmonary auscultation, weight)
- Vital Signs (HR, BP, RR)
- Dyspnea evaluation
- Fluid Ins and Outs since last reading
- Hemodynamics:
 - CVP
 - PA Systolic
 - PA Diastolic
 - PA Mean
 - PCWP
 - SvO2 as measured by the PA catheter
 - SaO2 as measured by pulse oximeter
- Echocardiogram
- Blood and urine labs per Appendix A
- Document any medication changes and adverse events

If the congestion target timepoint overlaps with a scheduled assessment (e.g, an every 24 hour hemodynamic measurement), the scheduled assessment value can be used and also entered on the congestion target met timepoint eCRF.

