5.4 Additional Data to be Reported

- Rate of occurrence of all adverse events;
- Utilization of continuous renal replacement therapy (CRRT), ultrafiltration and dialysis;
- Change in serum creatinine;

- Change in eGFR;
- Change in diuretic doses;
- Change in urine sodium excretion;
- QoL changes from KCCQ and EQ5D;
- Change in dyspnea assessment;
- Changes in echo parameters (includes CO);
- Changes in cardiac output and cardiac power output;
- Rates of hemolysis as measured by Lactate Dehydrogenase (LDH), Plasma Free Hb (pfH) and urine hemoglobin.

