7.9.2 Laboratory assessments

Laboratory measurements will be listed and summarized for actual values and change from baseline with descriptive statistics for As-Treated and PSC populations by Timepoint (Day of Implant, Congestion Target Met, Post 72Hrs or Discharge and Follow-Up). Laboratory measurements will be separated into two categories – Blood Labs and Urine Labs.

Additional summary for lactate dehydrogenase (LDH), plasma free Hb (pfH) and urine hemoglobin will be provided for the As-Treated and PSC populations by Timepoint (Day of Implant, Congestion Target Met, Post 72Hrs or Discharge and Follow-Up).

In addition to the collected laboratory measurements, the following derived parameters will be listed and summarized as the part of Urine Labs category (with the Date/Time of measurement and Timepoint as for corresponding Albumin and Creatinine evaluations):

$$\text{UACR (mg/g)} = \frac{\text{Urine Albumin (mg/dL)}}{\text{Urine Creatinine (g/dL)}}.$$

Laboratory measurements (except for Blood Labs evaluations of Blood Urea Nitrogen and Creatinine) collected from the time of implant until Post 72Hrs or Discharge will be presented graphically by patient for As-Treated and PSC populations.

Blood Labs measurements of Blood Urea Nitrogen and Creatinine collected from the time of implant until Follow-Up will be presented graphically by patient for As-Treated and PSC populations.

Boxplots of Blood Urea Nitrogen and Creatinine will be provided by subgroup and overall to compare baseline results with Congestion Target Met and Follow-Up for As-Treated population.

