7.9.3 Vital signs

Vital signs, including measurements of respiratory rate (breathes per minute), heart rate (beats per minute), and BP (mmHg), will be listed and summarized for actual values and change from baseline with descriptive statistics for the As-Treated and PSC populations by Timepoint (Baseline Monitoring, Day of Implant, Congestion Target Met, Post 72Hrs or Discharge and Follow-Up).

Vital signs measurements collected from the time of implant until Post 72Hrs or Discharge will be presented graphically for each patient and each parameter for As-Treated and PSC populations.

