7.9.4 Cardiovascular Examination

Cardiovascular examination measurements will be listed and summarized by Timepoint (Pre-Implant, Day of Implant, Congestion Target Met, Day of Retrieval, Post 72Hrs or Discharge and Follow-Up) with descriptive statistics for the As-Treated population by subgroup and overall.

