7.9.5.1 Cardiac Output and Cardiac Power Output

Cardiac Output (CO) and Cardiac Power Output (CPO) are derived parameters that will be associated with hemodynamic measurements of SaO₂ and SvO₂ (including date and time). Calculations will be based on the last non-missing measurements of Height, Weight, Blood Hemoglobin (BH), Systolic and Diastolic Blood Pressure at Baseline and Once Congestion Target is Met.

Cardiac Output (mL/min) is calculated as:

$$\text{Cardiac Output} = \frac{\text{O}_2 \text{ consumption}}{\text{Arteriovenous O}_2 \text{ difference}} = \frac{125 \left[\frac{\text{ml O}_2}{\text{min m}^2} \right] * \text{BSA}}{13 * \text{BH} * (\text{S}_a\text{O}_2 - \text{S}_v\text{O}_2)},$$

where Body Surface Area (BSA) is calculated through Haycock's formula:

$$\text{BSA} = 0.024265 * (\text{Height [cm]})^{0.3964} * (\text{Weight [kg]})^{0.5378}.$$

Cardiac Power Output (W) is calculated as:

$$\text{Cardiac Power Output} = \frac{\text{Mean Arterial Pressure} * \text{Cardiac Output}}{451},$$

where Mean Arterial Pressure is calculated by:

$$\text{Mean Arterial Pressure} = \frac{\text{Systolic Blood Pressure} + 2 * \text{Diastolic Blood Pressure}}{3}.$$

Summary of CO and CPO at Baseline and Once Congestion Target is Met will be provided along with summary of change from Baseline to Once Congestion Target for As-Treated and PSC populations.

Detailed listing of CO and CPO will be provided along with all associated measurements for As-Treated and PSC populations .

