7.9.7 Echo parameters

Echo parameters will be listed and summarized by Timepoint with descriptive statistics the for As-Treated population by subgroup and overall.

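### The SAP lists changes in echo parameters as an outcome but plans only by-timepoint summaries, so the within-patient change and its SD are never tabulated; body weight has the same gap

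*SAP*

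**What the plan says.** **Echo.** The additional data in SAP 5.4 include "Changes in echo parameters (includes CO"; Protocol 3.3.4 has the same item. The analysis is in SAP 7.9.7: "Echo parameters will be listed and summarized by Timepoint with descriptive statistics", for the As-Treated population, by ejection-fraction subgroup and overall. It feeds Table 14.3.6.3.

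**Weight.** Protocol 4.5 says the duration of pump use should follow the physician's "target for diuresis (net fluid and weight loss". Weight is recorded as part of the exam that Protocol 4.5.3 calls "Cardiovascular exam (edema, pulmonary auscultation, weight". SAP 7.9.4 says "Cardiovascular examination measurements will be listed and summarized by Timepoint" and names six timepoints, from pre-implant to follow-up. It feeds Table 14.3.6.2.

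**Neighbouring sections.** SAP 7.9.2 reads "Laboratory measurements will be listed and summarized for actual values and change from baseline". SAP 7.9.3 says that vital signs (respiratory rate, heart rate and blood pressure, not weight) "will be listed and summarized for actual values and change from baseline with descriptive statistics". SAP 7.9.5 plans a summary of change for CVP, PCWP and PA pressures. SAP 7.9.5.1 does so for derived cardiac output and cardiac power output, "along with summary of change from Baseline to Once Congestion Target for As-Treated and PSC populations".

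**The concern.** The listed echo outcome is a change, and a change belongs to a patient. Two columns of group means give it only if the same patients stand in both columns, and even then they do not show how much patients varied in their change.

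Two things are at stake. First, if patients with a missing later value differ at baseline from the rest, the later mean moves for that reason alone, and a reader of the table cannot separate this from a device effect. Second, SAP 2.3 says the study should inform the design of later studies. The SD of change is a usual input for such a design, and it cannot be worked out from two timepoint SDs without the within-patient correlation, which no planned table gives.

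**Working it through.** The documents give no SD, correlation, precision or power for echo parameters or weight, so there is no stated figure to reproduce. The check is a comparison of sections, followed by illustrations under stated assumptions.

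**1. Which measures get a planned change summary?**

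| Measure | SAP section | Change planned? |
|---|---|---|
| Laboratory values | 7.9.2 | Yes |
| Vital signs | 7.9.3 | Yes |
| CVP, PCWP, PA pressures | 7.9.5 | Yes |
| CO and CPO derived from SaO2 and SvO2 | 7.9.5.1 | Yes |
| Hourly fluid and urine rates | 7.8.3.1 | Yes |
| Echo parameters, including echo CO | 7.9.7 | No |
| Weight (cardiovascular exam) | 7.9.4 | No |

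**2. Does another section fill the gap?** No.
- The general rule in SAP 3.2 gives mean, median, SD, minimum and maximum, without a change score.
- The CO in 7.9.5.1 is computed from oxygen saturations, so it is not the echo CO.
- Elsewhere in the SAP, weight is a baseline characteristic (7.2) and an input to body surface area (7.9.5.1).
- SAP 7.14 declares one departure from the protocol, on the urine-output timepoint. It says nothing about echo or weight.

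**3. Can the timepoint means come from different patients?** Yes. Protocol Appendix A schedules echo twice: at baseline, and once the congestion target is met or therapy is deemed ineffective. Before an unplanned retrieval, Protocol 4.5.1 asks only for hemodynamics, laboratory tests and a fluoroscopic image. Such a patient can have a baseline echo and no later one. Weight is less exposed, because it is also scheduled every 24 hours on therapy, at 72 hours or discharge, and at 30 days.

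**4. Complete pairs.** If all n patients have both values, mean(later) − mean(baseline) = mean(later − baseline). The mean change can be read from the table, but its SD cannot.

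**5. Incomplete pairs, with no patient changing (illustration).** Assume 30 patients at baseline, of whom 6 have no later echo, and let the LVEF of those 6 lie 10 points below the mean of the other 24.
- Baseline mean of all 30 = mean of the 24 − 10 × 6/30 = mean of the 24 − 2.0.
- Later mean = mean of the 24.
- Apparent rise = **2.0 points**.

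If the 6 lie 10 points below the mean of all 30 instead, the rise is 10 × 6/24 = 2.5 points.

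**6. The SD of change (illustration).** With equal SDs at both timepoints and within-patient correlation r, SD of change = SD × √(2(1 − r)).
- LVEF, assumed SD 15 points: r = 0.6 gives 15 × √0.8 = 13.4; r = 0.9 gives 15 × √0.2 = 6.7.
- Weight, assumed SD 25 kg: r = 0.9 gives 25 × √0.2 = 11.2 kg; r = 0.98 gives 25 × √0.04 = 5.0 kg.

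A later study's sample size, if based on mean change, scales with 1 − r. Over these ranges it stays uncertain by a factor of 0.4/0.1 = 4 for LVEF and 0.10/0.02 = 5 for weight.

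**7. What a reader loses by treating the two columns as independent (illustration, n = 30 pairs).** SE unpaired = SD × √(2/30); SE paired = SD × √(2(1 − r)/30).
- LVEF: 3.87 points unpaired, against 2.45 (r = 0.6) to 1.22 (r = 0.9) paired.
- Weight: 6.45 kg unpaired, against 2.04 (r = 0.9) to 0.91 kg (r = 0.98) paired.

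**The case against.** The case on the other side has five parts.

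- **The protocol covers it in general terms.** Protocol section 7 says each patient's data will be reviewed individually and gives absolute and relative changes as examples of the planned summaries. SAP section 1 says the SAP is read together with the protocol. However, the protocol names no variable there, and the SAP, which does name them, leaves out echo and weight.
- **The data are not lost.** Listings 16.2.10.3 and 16.2.10.4 show each patient's exam and echo values, and with at most 30 patients the changes can be derived by hand. This stands: the change is untabulated, not irrecoverable. A listing still does not replace a planned table for a listed outcome.
- **Precision.** A reader might infer from step 7 that the plan throws away precision several-fold. The documents do not support that. No test, interval or standard error is planned for echo or weight, so the loss falls only on someone who compares the columns as if they were independent. The correlations are also assumed. For echo they may be lower, because Protocol 4.3 leaves technique and views to the institution and accepts an earlier echo from the same hospitalization.
- **Weight.** A reader might infer that weight change is an outcome left without an analysis. It appears in neither Protocol 3.3.4 nor SAP 5.4. The case for tabulating it is its role in the diuresis target, which is weaker than the case for echo.
- **Missing patients.** The target-met assessment also covers therapy deemed ineffective, so chiefly unplanned retrievals would miss it. The documents do not say how many to expect.

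**Conclusion.** The gap holds. SAP 5.4 lists a change in echo parameters, and no planned table reports that change or its SD. Weight is handled in the same way, although the SAP does plan change summaries for laboratory values, vital signs and hemodynamics.

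The consequence is limited. With complete pairs only the SD of change is missing. With incomplete pairs the timepoint means can shift without any patient changing, by 2.0 LVEF points in the example. That figure rests on an assumed count of 6 missing and an assumed 10-point difference; the SDs and correlations in steps 6 and 7 are assumptions too. These figures show possible size and do not predict what the trial will find.

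No primary endpoint is affected and the study is descriptive, so the point is minor. It is worth acting on because the data are already collected and the correction costs almost nothing.

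**What to change.** - **SAP 7.9.7 and Table 14.3.6.3, continuous echo parameters; SAP 7.9.4 and Table 14.3.6.2, weight.** Add the within-patient change from baseline to each later summarised timepoint, in patients with both values: number of pairs, mean, SD, median, minimum and maximum. Beside it, show the baseline summary for those same patients. SAP 7.9.2 and 7.9.3 do not specify that last element, so it has to be written out.
- **Baseline.** Use the definition in SAP section 4. For weight this is the Baseline Monitoring value, although weight is measured again on the day of implant. If the day-of-implant value is preferred, name it explicitly as an exception, so that two baselines do not coexist.
- **Valve regurgitation grades (AR, TR, MR).** Use a shift table of baseline against later grade, because a mean and SD of change does not suit ordered grades.

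The cost is SAP wording and extra columns in two tables, plus the shift table. No new data are needed.

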6 ANALYSIS POPULATIONS AND SUBGROUPS

6.1 Analysis Populations

The following populations will be considered for the study:

6.1.1 All Enrolled Population

The All Enrolled population will be defined as all patients who signed the ICF. The All Enrolled population will be used in disposition outputs and/or outputs related to patients' eligibility and partial Safety analysis.

6.1.2 Intent-to-Treat (ITT) Population

The ITT population will be defined as all enrolled patients that have an attempted implant whether or not successful. This population will be used for demographic and partial safety analyses.

6.1.3 As-Treated Population

The As-Treated population will be defined as all enrolled patients with the pump implanted (hemostasis achieved). This population will be used for partial demographic analysis as well as all safety and efficacy analyses.

6.1.4 Pump Speed Changes (PSC) Population

The PSC population will be defined as all enrolled patients with the pump implanted in whom pump speed changes occurred during Aortix Therapy. This population will be used for additional analysis of Laboratory assessments, Vital signs, Hemodynamic parameters and Urine Output measurements.

6.1.5 Diuretic Equivalents Analysis Population

The Diuretic Equivalents Analysis population will be defined as all enrolled patients with the pump implanted who during Baseline and Aortix Treatment analysis periods (see [Section 7.4.2](#)) have

received diuretics that are specified in Medication Memo for converting to furosemide equivalents. Patients who during specified analysis periods have not received any diuretics or received diuretics that are not specified in Medication Memo will be excluded. This population will be used for the analysis of furosemide equivalents.

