After signing informed consent, a urinary collection device will be placed, if not already present. A Foley catheter is recommended, but an external urine collection device may be used per institution requirements. The urine collection device will be placed (do not measure the urine collected during catheter placement) at least twelve (12 hours) before the Aortix Pump placement. If a urinary collection device is already in place, urine should be discarded. Output and intake should be strictly observed starting twelve hours prior to the scheduled implant. The urine collection device and the strict ins/outs monitoring will continue until the Aortix pump is retrieved. The first measurement of intake and output should occur at least six hours prior to Aortix placement and should be recorded every two hours until the pump is turned on. Measurements will occur at the frequency outlined in **Appendix A**.

Fluid ins should be monitored (IV and Oral) for the entire duration the urine collection device is in place with final measurements taken at the time of device retrieval.

Patients will receive standard medical therapy throughout the study. Patients should be on optimized medical therapy prior to being considered for Aortix Pump placement. To characterize the effect of the experimental device, physicians should not adjust the diuretic or inotrope dosing regimen during the twelve (12) hours prior to or the twelve (12) hours after Aortix Pump placement, unless medically necessary. **Diuretics and inotropes should not be adjusted for twelve (12) hours after the Aortix pump is turned on, however, after that point, while the Aortix pump is running, cessation of medications or down titration of diuretics, inotropes or other medications are allowed.** Adjustments of medical therapy can otherwise be made at any point during the study period at the discretion of the treating physician. All medications and medications adjustments will be captured on eCRFs.

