7.4.2 Loop Diuretic – Analysis of Furosemide Equivalents

There will be 2 analysis periods defined:

- Baseline analysis period – from 48 prior to the start of Aortix treatment until the start of Aortix treatment.
- Aortix Treatment analysis period – from the start of Aortix treatment until the end of Aortix treatment.

For the pre-specified list of loop diuretics (which are defined by Medication Memo) an average daily dose of corresponding medication received during the specified analysis period will be derived for the Baseline analysis period and Aortix Treatment analysis period. In cases when start/stop date is incomplete the maximum possible duration of medication treatment will be used for derivation of the average daily dose.

An average daily dose of each specified medication will be converted to furosemide equivalents (per Medication Memo) and the Total Average Daily Dose of Furosemide Equivalents (mg) will be derived as the sum of all converted average daily doses. If there are no diuretics received from a pre-specified list of loop diuretics (which are defined by Medication Memo) during the analysis period (Baseline or Aortix Treatment) then the Total Average Daily Dose of Furosemide Equivalents will be set to 0.

Summary of Total Average Daily Dose of Furosemide Equivalents (mg) at Baseline analysis period and Aortix Treatment analysis period will be provided along with the summary of change from Baseline analysis period to Aortix Treatment analysis period.

Specified derivations and analysis will be conducted only for the Diuretic Equivalents Analysis population.

The list of medications will correspond to the latest version of Medication Memo.

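### The Diuretic Equivalents population, read plainly, leaves the SAP's zero-dose rule with no patient to apply to and selects patients on the on-pump dose being summarised

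*SAP*

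**What the plan says.** SAP 6.1.5 defines the Diuretic Equivalents Analysis population as "all enrolled patients with the pump implanted who during Baseline and Aortix Treatment analysis periods" received diuretics that the Medication Memo lists for conversion. It then states the exclusion: "Patients who during specified analysis periods have not received any diuretics or received diuretics that are not specified in Medication Memo will be excluded". It does not say whether a listed diuretic is needed in each period or in at least one of them.

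SAP 7.4.2 covers the case of no listed loop diuretic in a period: "during the analysis period (Baseline or Aortix Treatment) then the Total Average Daily Dose of Furosemide Equivalents will be set to 0". The same section limits the scope: "Specified derivations and analysis will be conducted only for the Diuretic Equivalents Analysis population". Its treatment period covers the whole time on the pump, "from the start of Aortix treatment until the end of Aortix treatment", and its Baseline period is the 48 hours before that.

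Protocol 4.5 says: "Diuretics and inotropes should not be adjusted for twelve (12) hours after the Aortix pump is turned on". Protocol 4.3 makes an exception for medical need and says that after this point "cessation of medications or down titration of diuretics, inotropes or other medications are allowed". Protocol 4.3 also asks for diuretics to be left unadjusted for the 12 hours before implant. Change in diuretic doses is listed among the other data to be reported (Protocol 3.3.4, SAP 5.4); it is not a primary endpoint.

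**The concern.** The zero rule exists so that a patient with no loop diuretic in one period still contributes a change. The population rule, on its plain wording, removes that patient before the zero can be assigned. A patient whose on-pump dose is 0 has the largest possible fall from his or her baseline, so whether the patient counts would depend on the result itself. The second limb of the exclusion adds a further problem. Read literally, any unlisted diuretic removes a patient whose listed loop dose is perfectly well defined. Two programmers could build different populations from this text, and Table 14.1.3.4 is the only planned table titled for furosemide equivalents.

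**Working it through.** The plan gives no dose, count or power figure on this point, so there is nothing to reproduce. The check sets the two sections side by side, asks which patients are at risk, and sizes the effect under stated assumptions.

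**1. Do 6.1.5 and 7.4.2 fit together?** Take patients with no unlisted diuretic and list the four possible patterns.

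| Listed diuretic at Baseline | Listed diuretic on pump | In population if *each* period is required | In population if *either* period suffices | Zero rule needed |
|---|---|---|---|---|
| yes | yes | yes | yes | no |
| yes | no | no | yes | yes, pump period |
| no | yes | no | yes | yes, Baseline |
| no | no | no | no | yes, both |

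With *each*, the zero rule applies inside the population in 0 of 4 patterns. With *either*, it applies in 2 of 4, and only patients with no listed diuretic at all are left out.

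**2. The unlisted-diuretic limb.** Take a patient on a listed loop diuretic at Baseline and only an unlisted diuretic on the pump. SAP 7.4.2 gives 0 mg for the pump period. SAP 6.1.5, read literally, excludes the patient, even if one listed diuretic in either period is otherwise enough. A patient on a listed loop diuretic throughout plus an unlisted add-on is excluded in the same way. Protocol 4.3 records thiazide diuretics and MRAs as categories of their own, so such combinations are foreseen. The Memo is not among the documents, so which drugs are unlisted is unknown.

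**3. Who has no listed diuretic on the pump?** Suppose a constant daily dose is stopped at hour 12 of T days of therapy. The average on-pump dose as a share of baseline is 12 / (24 × T):

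- T = 1: 50%
- T = 2: 25%
- T = 4: 12.5%
- T = 7: 7.1%

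All are above 0, so this patient stays in under both readings. Only a patient with no listed diuretic during the entire pump period is at risk. The documents leave some routes to that. The Baseline window is 48 h and the pre-implant freeze only 12 h, so a drug given in the first 48 - 12 = 36 h of the window can count at Baseline and be stopped before the freeze. A drug may also be stopped at once for medical need, or be given intermittently with no dose after pump start.

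**4. Size, as an illustration.** Assume 30 implanted patients, each with baseline dose indexed to 100. Let k patients have no listed diuretic on the pump (change -100) and let the others change by r. The mean with the k patients kept is [k × (-100) + (30 - k) × r] / 30; with them dropped it is r.

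| k | kept, r = 0 | dropped, r = 0 | kept, r = -25 | dropped, r = -25 |
|---|---|---|---|---|
| 1 | -3.3 | 0 | -27.5 | -25 |
| 3 | -10.0 | 0 | -32.5 | -25 |
| 6 | -20.0 | 0 | -40.0 | -25 |
| 10 | -33.3 | 0 | -50.0 | -25 |

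Dropping these patients understates the reduction. The mirror pattern (nothing at Baseline, 100 on the pump) acts the other way: with 3 of each among 30 and the others unchanged, the mean is (-300 + 300) / 30 = 0, the same as with all six dropped.

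**The case against.** The strongest reply is that the text can be read so that it works. The exclusion can mean no diuretics across the two periods together, and the unlisted limb can mean unlisted diuretics only. The zero rule names Baseline or Aortix Treatment as alternatives, which has an effect only on the either-period reading. This stands as a possible reading, and a reader who infers that the two sections contradict each other on any reading goes too far. But the conjunction in 6.1.5 points to both periods, and the literal unlisted limb conflicts with 7.4.2 even when either period suffices. The SAP has to say which is meant.

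A reader might also infer that every patient whose diuretics are stopped on the pump is dropped. The documents do not support that: the 12 h freeze, with a treatment period counted from pump start, normally leaves such a patient with a non-zero average dose and membership.

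Nor do they support a bias in a known direction. Patients with no loop diuretic at Baseline but some on the pump are lost too. Inclusion criterion 2 and Protocol 4.1 call for 48 hours of intravenous diuretics before enrollment, which should make that pattern less common. It cannot be ruled out, because no maximum gap from enrollment to implant is stated. The effect of losing add-on patients is unknown.

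Finally, there are safeguards. SAP 7.4 summarises diuretic doses for all As-Treated patients by timepoint, SAP 7.1 reports population sizes and membership, and Protocol 7 has each patient's data reviewed individually. These make the problem visible and limit the harm. They are only a partial backup, since the SAP 7.4 summary does not mention furosemide equivalents.

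**Conclusion.** The point holds as a defect of definition. On the plain reading of SAP 6.1.5 the zero rule in 7.4.2 can never apply, and the furosemide-equivalent change is summarised in a set chosen partly by the on-pump dose. Those who could be lost are patients with no listed diuretic for the whole pump period and patients who also took an unlisted diuretic. Their number and the net direction of bias cannot be determined from the documents. The move from 0% to -10% of baseline for 3 patients in 30 rests on equal baseline doses, no change in the others and no patients of the mirror pattern; it shows scale and is not an estimate. The outcome is descriptive additional data with no test attached, so no primary conclusion is affected. It is still worth correcting before the table is programmed. The parallel inotrope analysis in SAP 7.4.3 uses the As-Treated population without such a restriction.

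**What to change.** Reword SAP 6.1.5 so that:

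- the population is all As-Treated patients who received at least one Memo-listed loop diuretic in either the Baseline or the Aortix Treatment period;
- the 7.4.2 zero rule applies to the other period where it has no listed loop diuretic;
- a concurrent unlisted diuretic does not exclude a patient: only the listed drugs are converted, and the others are flagged in the listing;
- the number of implanted patients excluded, and the reason, is shown with Table 14.1.3.4.

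Defining membership by the Baseline period alone would be less suitable. It would leave the Baseline half of the zero rule unused and drop patients who first receive a loop diuretic on the pump, which removes increases in dose.

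The cost is SAP wording only; no new data are needed.
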